- **Recruitment and Informed consent:** Study participants will be asked to sign an informed consent approved by the Institutional Review Board of the VAMC. This includes a clear description of the study and its objectives, the number of patient contacts and procedures, the information to be collected, the tests (induced sputum) to be performed, possible benefits and risks to the patient, and permission to use the patient's health plan medical record data. The subjects will be informed that remaining sample would be used for future studies.
- **Protections against Risk:** We will take special precautions to protect the security of the research data. These include authorization to send and receive data, verification of identity, and encryption of all data. We will follow institutional guidelines on data access and security. Rigorous policies will be followed for maintaining secure backups for all research data and complete documentation of data files, both locally and centrally. All data processing procedures will be carefully documented and reviewed periodically.

All patients identified for inclusion in the research project will be assigned a unique study identification number. Prior to any data transfer, all identifiers (e.g., names, medical record numbers, health plan enrollee numbers, etc.) will be removed. We will also utilize password protection programs for all computerized records. In no instances will identifying information, either for patients or health plans, be publicly disclosed.

All study staff will be trained and reminded to appreciate the confidential nature of research data. Each investigator and staff member involved in the proposed study will sign a confidentiality agreement annually and be required to have participated in required IRB training.

Risk to patient confidentiality. Confidential information will be collected as part of this study. Safeguards will be taken to protect this information. Source documents will be kept in a locked cabinet in a locked room. All electronic data will be stripped of personal identifiers. The database will be password-protected and stored in a secured network drive behind the VA firewall. Only the study team will have access to the source documents and the electronic data.

Potential Benefits of the Research to the Subject and Others

A possible future benefit is that the research may improve health care for themselves and other patients with similar diseases.

References:

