Date: 3/31/2014
NCT: NCT02252588

STUDY PROTOCOL

Title: The Effect of Chlorhexidine on the Oral and Lung Microbiota in Chronic Obstructive Pulmonary Disease

Investigators:

[name] Principal Investigator
[name]
[name]
[name]
[name]

A. Specific Aims

Aim 1. Determine the effect of twice-daily chlorhexidine oral rinse on oral and lung microbiota biomass in subjects with chronic obstructive pulmonary disease (COPD) with chronic bronchitis. Our primary outcome will be to compare the microbiota biomass (number of bacteria as measured by 16S rRNA copy number) of *induced sputum* and the *oral cavity* before and after 8 weeks of twice-daily chlorhexidine oral rinse (n=25) compared to controls (n=25) using qPCR and next-generation sequencing of the bacterial 16S rRNA gene comparing total bacterial biomass.

Our *hypothesis* is that 8 weeks of chlorhexidine oral rinse will decrease microbiota biomass compared to baseline and those on placebo. Furthermore, we hypothesize that chlorhexidine treatment will: i) decrease lung and oral microbiota diversity; ii) alter microbiota taxonomic composition in the lung and oral cavity; iii) decrease systemic inflammation as measured by blood high sensitivity C-reactive protein (hsCRP), fibrinogen and leukocyte count; and iv) demonstrate a trend towards improvement in respiratory health status as measured by the Breathlessness, Cough, and Sputum Scale (BCSS)[1, 2] and St. George's Respiratory Questionnaire (SGRQ).

Subaim 1: Determine if chlorhexidine alters the lung and oral rinse microbiota diversity and taxonomic composition. Our *hypothesis* is that chlorhexidine oral rinse will decrease the diversity (Shannon and inverse Simpson diversity indices) and taxonomic composition of both oral and lung microbiota compared to those on placebo as determined by next-generation sequencing of the bacterial 16S rRNA gene.

Subaim 2: Determine the impact of chlorhexidine on systemic inflammation. Our *hypothesis* is that the decrease in lung microbiota biomass is associated with a decrease in systemic inflammation as measured by blood hsCRP, fibrinogen, and leukocyte count.

Subaim 3: Determine if respiratory symptoms associate with the lung microbiota biomass. Our *hypothesis* is that chlorhexidine will demonstrate improved respiratory health status as measured by the BCSS and SGRQ.

B. Background and Significance

COPD and Chronic Obstructive Bronchitis are major health concerns

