The potential benefit of oral decontamination in the treatment of COPD remains unknown. We have compelling evidence that the COPD lung microbiota is more diverse than healthy lungs and is a reflection of the oral microbiota, presumably due to repeated aspiration and decreased clearance. In addition, it is well established that bacteria are a major cause of COPD exacerbations. Therefore, it seems plausible that the oral microbiota is a major contributor in COPD and especially in COPD exacerbations. Chlorhexidine is a broad-spectrum antiseptic that is safe, well-tolerated and shown to decrease respiratory infection associated with oral intubation. We hypothesize that twice daily oral rinses with chlorhexidine will result in a decrease in the lung microbiota biomass. If proven correct, this would be the basis for a large interventional trial to determine if oral decontamination with chlorhexidine will decrease COPD exacerbations.

C. Work Proposed

Overview

The *primary outcome* of this pilot study is to determine if twice-daily chlorhexidine oral rinse decreases the microbiota biomass, as measured by 16S rRNA copy number, in the COPD lung and oral cavity as measured in induced sputum and oral wash. Our *secondary outcome* are to determine if chlorhexidine oral rinse: i) decreases lung and oral microbiota diversity; ii) alters taxonomic composition of the lung and oral cavity microbiota; iii) decreases systemic inflammation as measured by blood hsCRP, fibrinogen and leukocyte count; and iv) changes in respiratory health status as measured by the BCSS and SGRQ. If our hypotheses are supported, this study will form the basis of an interventional trial to determine if altering the oral microbiota with chlorhexidine can prevent COPD exacerbations.

Study Design Overview

This study will determine if the microbiota of the oral cavity and induced sputum is altered by twice-daily chlorhexidine rinse. At *baseline*, the following studies will be done:

1. Spirometry to determine study eligibility and to guide sputum induction protocol.
2. Oral rinse and induced sputum for microbiota analysis. An oral rinse of 15 ml sterile water and induced sputum will be obtained at baseline for microbiota analysis.
3. Inflammatory markers (blood hsCRP, fibrinogen, and leukocyte count).
4. Breathlessness, Cough and Sputum Scale (BCSS). This 3-item self-completed questionnaire focuses on common COPD symptoms.

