The first two questions of the SGRQ comprise eligibility criteria for the study (see inclusion criteria). If subjects are randomized in the study, they will be asked to complete the entire SGRQ as part of the baseline visit and again at completion of the study intervention. The SGRQ is a self-administered questionnaire that was developed to measure health-related quality of life specifically related to pulmonary disease. Since its development, it has been validated for use in many chronic lung diseases, including COPD[25]. The SGRQ contains 11 questions that ask for a scaled answer (from 1 to 5), 39 questions that ask for true/false answers and one free-text answer. A copy of the SGRQ is attached to this proposal. Subjects can complete the SGRQ in approximately 10-15 minutes. The questions evaluate three areas or domains: respiratory symptoms, activity limitations from breathlessness, and impact of respiratory disease on social and psychological functioning. The SGRQ is scored on a scale of 0 to 100, with a score of 100 reflecting the most severe symptoms, activity limitations and psychosocial impact. The minimum clinically important difference in the SGRQ is widely accepted as being 4 units[26].

Spirometry

Spirometry will be performed prior to randomization to ensure that participants meet eligibility criteria. Spirometry will be performed in compliance with standards jointly published by the American Thoracic Society and the European Respiratory Society[27]. Spirometry will be performed after patient inhales 2 puffs of albuterol (90 mcg/inhalation).

Eligible Subjects:

Laboratory Evaluation

After obtaining informed consent and determining the participant is otherwise eligible for the study, the patient will undergo an oral rinse with sterile water (rinse for 30 seconds and collect expectorant) and sputum induction. The oral rinse and 2 ml of sputum will be used for the microbiota evaluation.

The blood draw will be performed by the VA laboratory or the study personnel. Blood will be sent to the VA laboratory to measure hsCRP, fibrinogen and leukocyte count. These biomarkers have been demonstrated to be predictive of COPD exacerbations[28].

Induced Sputum:

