At the conclusion of the study, we will censor any subject who reports using systemic antibiotics during the 8-week study period. This will prevent antibiotic use from confounding our microbiota results. As this study is a randomized controlled study, the analysis for the primary outcome will consist of testing for differences in changes in bacterial biomass between the two patient groups using a 2 sample *t*-test with equal variances between groups. While it is widely recognized that the *t*-test is robust with regard to departures from the normality assumption, if the data appear very non-normal (as observed in a *qq*-plot) even after standard transformations are considered (such as the Box-Cox transformation) then Wilcoxon's test will be used. Similarly, if the variance is markedly different between the groups then Welch's 2 sample *t*-test will be used. While randomization should ensure that the groups are balanced on important potential confounders (such as age) all such factors will be examined to check that there are not significant differences between the groups. If there are differences then linear models will be fit to account for these potential confounders (again, standard transformations will be considered to improve model fit and diagnostics will be performed to assess model assumptions).

The analysis for secondary endpoints necessarily takes a different strategy as that investigates the relationship among variables that are not subject to direct randomization. Hence the analysis will consider regression models that investigate how changes in health status (as measured by changes in the SGRQ) depend on microbial diversity and inflammatory markers. Model selection will be guided by scientific plausibility, model diagnostics and measures of model quality (such as AIC).

Sample Size and Power Calculation

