We can use the preliminary data on microbial diversity among COPD patients to estimate the power of the study. For concreteness we will assess the power for detecting a difference in the Simpson (1-D) diversity measure (the correlation between this measure and Shannon's measure was 0.96 in our preliminary data). The standard deviation in this measure among moderately affected COPD patients is 0.280 and is 0.298 among the severely affected COPD patients, and as there is no significant difference between the variances ($p=0.80$ by Bartlett's test) we combine the data from both groups and obtain an estimate of 0.281 for the standard deviation. To obtain an estimate of the magnitude of differences that are reasonable to expect from a drug that decreases the diversity of the lung flora, we fit a linear regression model with diversity as the outcome and age as the predictor variable (the ages range from 55 to 78 among these subjects). Age has a significant positive impact on diversity ($p=0.047$)

with an estimated slope of 0.017, so that over the course of 20 years the model predicts that there will be a change of 0.34 in diversity. Hence we investigated the power for values of the difference attributable to the effect of chlorhexidine from 0.22 to 0.32 and present the results in Table 1 (these results are from a 2 sample *t*-test with equal variance using the estimated standard deviation from the previous study and 20 subjects per group). These results indicate that the study should have acceptable power if chlorhexidine has an impact on the diversity of the lung microbiota that is comparable to what is observed due to the effect of aging. We will increase the sample size to 25 per group since we anticipate censoring at least 20% of the subjects because of antibiotic use during the study. This population has a demonstrated exacerbation rate of approximately 20% and exacerbations are often treated with antibiotics.

Effect size	0.22	0.24	0.26	0.28	0.30	0.32
Power	0.67	0.75	0.81	0.87	0.91	0.94

Table 1: The power of the study to detect a difference between the treatment groups as it depends on the magnitude of the difference in diversity between the 2 groups.

Quality Control

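### The health-status hypothesis predicts an undefined 'trend' in BCSS and SGRQ, and the analysis plan contains no between-arm comparison of either score by which to judge it

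*Combined protocol and SAP*

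**What the plan says.** The same hypothesis is worded in three ways.

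- **A. Specific Aims, Aim 1, hypothesis iv:** chlorhexidine will "demonstrate a trend towards improvement in respiratory health status as measured by the Breathlessness, Cough, and Sputum Scale (BCSS") and the SGRQ.
- **A. Specific Aims, Subaim 3:** "chlorhexidine will demonstrate improved respiratory health status as measured by the BCSS and SGRQ".
- **C. Work Proposed, Overview:** the secondary outcome is "changes in respiratory health status as measured by the BCSS and SGRQ", with no direction given.

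The Data Analysis Plan specifies a randomised comparison for the primary outcome: "testing for differences in changes in bacterial biomass between the two patient groups using a 2 sample *t*-test with equal variances between groups". For secondary endpoints it takes a different approach, "regression models that investigate how changes in health status (as measured by changes in the SGRQ) depend on microbial diversity and inflammatory markers". BCSS is not mentioned in that section.

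The section on the SGRQ supplies a benchmark, "The minimum clinically important difference in the SGRQ is widely accepted as being 4 units", but nothing links it to hypothesis iv. After listing the primary and secondary outcomes, the Overview concludes: "If our hypotheses are supported, this study will form the basis of an interventional trial".

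**The concern.** Whether the rinse changes symptoms is a question about a randomised treatment, and SGRQ and BCSS are both collected before and after treatment in both arms. The plan explains its secondary analysis by saying that it relates variables that were not themselves randomised. That suits the association between SGRQ and the microbiota, but it leaves the treatment effect on SGRQ and BCSS without an estimator, a test or an interval. All that remains for judging hypothesis iv is the word trend, which is undefined: no error rate, no minimum difference, no stated comparator, and no rule for one score against both.

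What is at stake is how the symptom result is reported. A small favourable difference, compatible with no effect or with mild harm, could be written up as support for the hypothesis without departing from the protocol. What counts as a trend could also be settled after the data are seen.

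**Working it through.** **Inputs from the documents.** Sample Size and Power Calculation: 20 analysable subjects per arm, 25 enrolled per arm after allowing for 20% censoring, and a diversity SD ("obtain an estimate of 0.281 for the standard deviation"). Section on the SGRQ: 4-unit minimum important difference.

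**Assumptions, not in the documents.** SD of SGRQ change 10 to 15 units; correlation between the SGRQ and BCSS arm differences 0.0 to 0.9; normally distributed arm differences.

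**1. The plan's own power figures.** Two-sample equal-variance *t*-test, noncentral *t*, two-sided 0.05, n = 20 per arm, SD 0.281:

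| Difference | 0.22 | 0.24 | 0.26 | 0.28 | 0.30 | 0.32 |
|---|---|---|---|---|---|---|
| Table 1 | 0.67 | 0.75 | 0.81 | 0.87 | 0.91 | 0.94 |
| Recomputed | 0.675 | 0.749 | 0.814 | 0.867 | 0.908 | 0.939 |

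The table reproduces, and so does 20/(1 − 0.20) = 25. The documents state no alpha; two-sided 0.05 is inferred from this match. These are the only power figures given, and they concern diversity. There are none for SGRQ or BCSS.

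**2. Trend read as the sign of the arm difference, inert rinse.** With no effect, the difference in mean change is symmetric about zero, so P(favourable) = 0.50 on one score (simulation at 20 per arm: 0.499). For two scores with correlation ρ, P(both favourable) = 1/4 + arcsin(ρ)/(2π):

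| ρ | 0.0 | 0.3 | 0.5 | 0.7 | 0.9 |
|---|---|---|---|---|---|
| Both favourable | 0.250 | 0.298 | 0.333 | 0.373 | 0.428 |

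Hypothesis iv joins the two scores with 'and', so the 25-43% row is closest to its wording.

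**3. Trend read as two-sided p<0.10 in the favourable direction.** The null rate is 0.10/2 = 5% per score.

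**4. What a favourable sign tells us.** The likelihood ratio, benefit against no effect, cannot exceed 1/0.50 = 2 on one score. For a true 4-unit SGRQ benefit, SE = SD × √(2/20), which is 3.16 at SD 10 and 4.74 at SD 15. P(favourable) = Φ(4/SE) = 0.897 and 0.800, so the ratio is 0.897/0.50 = 1.79 and 0.800/0.50 = 1.60. For a true 2-unit worsening, P(favourable) = Φ(−2/SE) = 0.264 and 0.337.

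**5. What an interval would show.** The 95% half-width is 2.024 × SE (*t*, 38 df), which is 6.40 units at SD 10 and 9.60 at SD 15. Both exceed 4 units. Two-sided 5% power for a 4-unit difference is 0.234 and 0.130.

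**The case against.** The strongest reply is that hypothesis iv is a forecast of what a small pilot may show and was never meant as a decision rule. That stands. A reader might infer that the hypothesis counts as met whenever the arm difference has a favourable sign, and that its false-positive rate is therefore 50%. The documents do not say so. Trend is undefined, and a sign-only rule is one reading among several. Requiring both scores gives 25-43%, and a p<0.10 reading gives 5% per score. If trend meant change from baseline within the chlorhexidine arm, the null rate need not be 50% at all. Subaim 3, which is devoted to this outcome, does not use the word trend.

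A reader might also infer that a symptom trend could by itself launch the next trial. The documents do not support that either. The section on efficacy of oral decontamination in COPD ties the larger trial to confirmation that lung biomass falls. The Overview sentence speaks of hypotheses in the plural and follows a list headed by biomass, and the future trial concerns exacerbations, not symptom scores. What remains is that the two statements of the basis for the next trial differ and should agree.

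It is also fair that the SGRQ figures rest on an assumed SD, and that a descriptive label with an estimate and interval is reasonable for a pilot. Neither point removes the gap: three wordings, no criterion, and no planned between-arm estimate of either score.

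**Conclusion.** The point holds as a gap in specification. The plan gives a vague prediction in place of an analysis of the randomised effect on BCSS and SGRQ, and so permits a non-significant favourable direction to be called support. Depending on how trend is read, an inert rinse would meet it anywhere from 5% of the time per score (p<0.10, favourable) to 50% (sign only, one score), with 25-43% for the sign on both scores. The 50% follows from symmetry of the between-arm difference; the 25-43% also needs the assumed correlation range. The interval widths, the power and the 2-unit worsening figures depend on the assumed SD of 10 to 15 units. The consequence is limited to the reporting of one secondary hypothesis in a pilot.

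**What to change.** 1. Use one wording in Aim 1 hypothesis iv, Subaim 3 and the Overview of Work Proposed, without the word trend.
2. Add to the Data Analysis Plan: *The chlorhexidine-minus-placebo difference in change in SGRQ and in BCSS will be estimated with 95% confidence intervals. The SGRQ interval will be read against the 4-unit minimum important difference. An interval that includes zero will be reported as inconclusive and not as support.* The planned regression can stay as an analysis of association.
3. Align the Overview sentence on the next trial with the biomass basis already given in the section on efficacy of oral decontamination.

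The cost is wording and two between-arm estimates from data already being collected. No patients or visits are added. The downside is that the pilot will most likely report the symptom result as inconclusive, since power for a 4-unit SGRQ difference is only about 13-23% under the assumed SDs.

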The sputum sample will be weighed and the oral wash volume will be measured. To identify the microbiota, DNA will be isolated from sputum and oral wash samples. Sputum samples will be treated with dithiothreitol (DTT) prior to isolation. We will use a previously described protocol for DNA isolation that includes bead beating to lyse bacterial cells, followed by precipitation with isopropanol and digestion with RNase. Samples will be subjected to PCR amplification using 16S rRNA gene primers specific to the constant regions flanking the V3 region[15, 29]. Amplicons will be gel purified and sequenced at the University of Minnesota Genomics Center using Illumina MiSeq equipment. To minimize effects of random sequencing errors, we will use RDP Pipeline to eliminate (a) sequences that did not appropriately match the PCR primer and the barcode at the beginning of a read, (b) sequence reads with <50 bases after the proximal PCR primer if they terminated before reaching the distal primer, and (c) sequences that contained more than one undetermined nucleotide (N). Both the proximal and distal primers will be trimmed from high-quality reads before database searches are performed.

Inflammatory Marker

To measure the inflammatory state, hsCRP, fibrinogen, and leukocyte count will be measured in blood.

Sample Banking

The microbiota studies will be performed at the University of MN. All remaining sample will be returned and stored in [name] laboratory at the VAMC. After completion, remaining sample will be stored for a maximum of 10 years for future confirmation studies and studies related to COPD. Samples will be de-identified and will be identified only by a pre-assigned sample ID number. Clinical data will NOT be given to the Univ MN laboratory.

Randomization procedure

Patients will be randomized via permuted block sizes of 2 to active drug or placebo in a ratio of 1:1. Because there is some evidence of an interaction with inhaled corticosteroids and the lung microbiota,

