we will stratify randomization according to use of inhaled corticosteroids at baseline. Only the Research Pharmacist will have access to the randomization list. The subjects will be instructed to use the study mouth rinse twice daily for 8 weeks as described above. The subjects will be asked to return all study medications at the last clinic visit. At the last visit the subjects will be asked whether they thought they were taking the active medication or placebo to assess the effectiveness of blinding.

The Breathlessness, Cough and Sputum Scale (BCSS)

The Breathlessness, Cough and Sputum Scale is an easy-to-use instrument for tracking the severity of respiratory symptoms and evaluating the efficacy of treatment in clinical trials in patients with COPD. It is designed as a daily diary in which subjects are instructed to answer three questions on a 0 to 4 scale, targeting breathlessness, cough and sputum. A total daily score is calculated from the question answers. This format allows investigators to assess symptom variability and trajectory over time. This tool has been validated in large clinical trials against the SGRQ[1, 2].

Monthly calls

Participants will be called at 4 weeks by the study coordinator to assess for: i) hospitalizations, ED visits; unplanned clinic visits; ii) new medication use including any systemic antibiotic use; iii) study drug compliance; iv) adverse events.

Effectiveness of blinding

At the last visit the subjects will be asked whether they thought they were taking the active medication or placebo to assess the effectiveness of blinding

Monitoring adverse events

Participants enrolled in this study will be monitored for adverse outcomes including adverse hospitalizations and death. Patients will be questioned during the mid-study telephone call and at the final study visit regarding any adverse drug reactions. In addition, participants will be given contact information for the study team and will be counseled to report any adverse effects. Participants will be questioned during the mid-study telephone call and at the final study visit regarding any hospitalizations. A report of every serious adverse event will be filed with the IRB per institutional policy. Electronic medical records will also be reviewed for 30 days after completing the study to capture any serious adverse outcomes, including hospitalization or death. If necessary, we will contact relatives or household members to obtain additional information.

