The risk to the participant is that of the *induced sputum*. Hypertonic saline sputum induction is a routine test performed in many clinical settings and clinical trials. It has been shown to be safe in the setting of COPD. We do not anticipate complications of chlorhexidine treatment since this is an ingredient in several over-the-counter products, including mouth washes, and chlorhexidine mouthwash is commonly prescribed following dental extractions. Listed below are potential complications.

1. Bronchospasm: Bronchospasm is the main reported complication of sputum induction with hypertonic saline and will be treated with albuterol either by metered dose inhaler or nebulized.
2. Intolerance to Chlorhexidine: Oral mucosal irritation and transient decrease in taste have rarely been reported with chlorhexidine. Mild tooth discoloration associated with concurrent tea ingestion has been reported.

A Data Safety and Monitoring Board (DSMB) will not be formed as part of this study since this is a small study with a short follow-up period.

Discontinuation of procedure

The procedure may be terminated at anytime for any of the following reasons:

- If the participant requests to withdraw from the study for any reason.
- If the investigators or the participant's physician believes the patient has experienced a serious adverse event that might be related to the study or that continued participation in the study might jeopardize the participant's medical care.
- The participant becomes so mentally or physically incapacitated that he/she can no longer make an informed judgment about continued participation in the study.

Unmasking of treatment allocation will occur in cases where such information is critical to ongoing care of the participant. At the conclusion of the study, the participants will be informed of treatment allocation.

Data Analysis Plan

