Members of the research team will become familiar with the study protocol and be trained in all procedural aspects. Patient recruitment and data acquisition will be performed principally by a trained and experienced study coordinator employed full-time by the Pulmonary Section of the Minneapolis VA Health Care System. [name] will supervise all aspect of the study. The study coordinator has expertise in performing spirometry, administering the questionnaires for this study, and in thorough documentation of study procedures.

Source documents will include paper case report forms, printouts from spirometry machines, printouts of laboratory data, original surveys completed by the participants and any outside (non-VA) medical records that are obtained. All data will be entered into a computerized database for statistical analysis, with retention of source documents for verification of all computerized data, should the need arise.

All electronic data will be stripped of personal identifiers and stored in secure network drives that are password-protected. Source documents will be secured in a locked file cabinet within a locked room for security. The only method to link electronic data to individual data will be a key linking participant name to study subject number.

Protection Against Risk

The risk to the participant of this study is small.

Induced Sputum: We will pre-treat with albuterol, either MDI or nebulizer, to prevent bronchospasm. Albuterol is a commercially available, FDA-approved drug. The common side effects associated with albuterol are mild, transient tachycardia, tremulousness, and nervousness. In addition, we will monitor peak flows and terminate the procedure for a significant drop. All bronchospasm will be treated with additional doses of albuterol.

Spirometry. The risks of spirometry are minimal. Some participants may experience temporary shortness of breath or lightheadedness as a result of deep and rapid breathing that is required to perform spirometry. These risks are small and spirometry is routinely performed in this patient population. Administration of albuterol prior to testing is also a standard procedure and is known to be

very safe. Albuterol is a commercially available, FDA-approved drug. The common side effects associated with albuterol are mild, transient tachycardia, tremulousness, and nervousness.

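### Fixed, published blocks of 2 within inhaled-corticosteroid strata mean that learning one participant's arm also reveals the block partner's arm

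*Combined protocol and SAP*

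**What the plan says.** The Randomization procedure section gives a single block size: "Patients will be randomized via permuted block sizes of 2 to active drug or placebo in a ratio of 1:1". It adds that "we will stratify randomization according to use of inhaled corticosteroids at baseline". Nothing in the document varies the block size or withholds it from site staff. Quality Control expects the research team to know the protocol, where the size is printed. Medications/Supplement Use has all medications, inhalers included, recorded for each participant, so the stratum is visible to the team.

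Two safeguards are described. The first is that "Only the Research Pharmacist will have access to the randomization list". The second, in Study Intervention, is a matched placebo rinse with blue dye and mint flavour.

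An arm can become known during the trial. Under Discontinuation of procedure, "Unmasking of treatment allocation will occur in cases where such information is critical to ongoing care of the participant". Under Monitoring adverse events, possible clues are described as uncommon: "Oral mucosal irritation and transient decrease in taste have rarely been reported with chlorhexidine".

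On staffing, Quality Control says "Patient recruitment and data acquisition will be performed principally by a trained and experienced study coordinator", and Monthly calls says "Participants will be called at 4 weeks by the study coordinator to assess for" health-care use, new medication including systemic antibiotics, compliance and adverse events.

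**The concern.** A block of 2 is the smallest possible at 1:1, and here the size is both constant and public. Restricting access to the list protects the list, but a constant pattern can be reconstructed from one known arm and the enrolment order.

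Concealment and masking are at stake at three points, all contingent on an arm being learned or inferred:

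- **Enrolment.** The coordinator who principally recruits is also the person who hears adverse-event reports at week 4. Foreknowledge could influence who is enrolled next in that stratum.
- **Questioning about adverse events and antibiotics.** The Data Analysis Plan removes anyone who reports systemic antibiotic use, and the sample-size section expects to lose at least 20% this way. How the question is asked therefore bears on who enters the primary comparison.
- **SGRQ and BCSS.** Participants complete these themselves, so staff knowledge could act only indirectly.

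**Working it through.** **Inputs.** Block size 2 and ratio 1:1, two strata (Randomization procedure); 25 per group, 50 in total; SD 0.281, 20 evaluable per group and differences of 0.22 to 0.32 (Sample Size and Power Calculation). A two-sided alpha of 0.05 is my assumption, as the document gives none.

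**1. The plan's own figures.** The plan gives no predictability figure, so the only one to reproduce is Table 1. For a two-sample t-test with 20 per group, the standard error is 0.281 × √(1/20 + 1/20) = 0.0889. At a difference of 0.22 the noncentrality is 0.22 / 0.0889 = 2.476 on 38 degrees of freedom. Power across the table is 0.675, 0.749, 0.814, 0.867, 0.908 and 0.939, against the printed 0.67, 0.75, 0.81, 0.87, 0.91 and 0.94. The inflation 20 / (1 − 0.20) = 25 per group also reproduces.

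**2. One known arm.** With A for active and P for placebo, the only blocks of 2 are AP and PA. Hence P(second arm known | first known) = 1, and the same holds in reverse. In a block of 4, after one allocation, two of the three remaining places belong to the other arm, so the second is predicted with probability 2/3 = 0.67.

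**3. One guessed arm.** Let q be the probability that the guess about the first member is right.

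- Blocks of 2: the prediction for the second member is right with probability q, so 0.60 stays 0.60 and 0.80 stays 0.80.
- Blocks of 4: q × 2/3 + (1 − q) × 1/3, which gives 0.53 for q = 0.60 and 0.60 for q = 0.80.

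Blocks of 2 pass the guess on undiluted but do not turn it into certainty.

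**4. Upper bound.** Enumerate every balanced block and count the places whose arm is fixed once all earlier arms in the block are known.

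| Block size | Balanced sequences | Determined places | Share |
|---|---|---|---|
| 2 | 2 | 2 of 4 | 50% |
| 4 | 6 | 8 of 24 | 33% |
| 6 | 20 | 30 of 120 | 25% |

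For 50 participants in strata of n₁ and 50 − n₁, blocks of 2 give floor(n₁/2) + floor((50 − n₁)/2) determined allocations. A 20/30 split gives 10 + 15 = 25; a 15/35 split gives 7 + 17 = 24. The table assumes that the block size is known. Withholding and varying it can only make prediction harder; I have not put a number on that gain.

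**5. Cost of larger blocks.** An incomplete last block of 6 can leave an imbalance of 3 in a stratum, so at most 6 over two strata. Among 40 evaluable participants that is 17/23. The standard error becomes 0.281 × √(1/17 + 1/23) = 0.0899 and the noncentrality 0.22 / 0.0899 = 2.448. Power is 0.665, against 0.675 for 20/20.

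**The case against.** The strongest reply is that this is a masked, single-centre pilot with a laboratory primary endpoint, and that an arm will seldom be learned. Much of that stands.

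- The rinse is matched, the list is restricted, and unmasking is reserved for cases where care depends on it. The document does not say who would learn an unmasked allocation.
- Irritation and taste change are called rare. Tooth discoloration is tied to tea, which participants are told to avoid.
- The next enrolment is foreseeable only if the known participant is first in a block whose second place is still open, and staff follow the order within the stratum. No accrual rate is given, so the frequency cannot be estimated. If the block is complete, the harm is unmasking of someone already enrolled; an unpaired last participant reveals nobody.
- Baseline samples and questionnaires precede randomization, and the Sample Banking section keeps clinical data from the sequencing laboratory.

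A reader might infer that a suspicion about one participant makes the partner's arm certain, that half of all allocations will in practice be known, or that the coordinator's encouragement to cough will bias the sputum specimens. The documents support none of these. A suspicion transfers only its own accuracy. The 50% needs every earlier arm in the block to be known, as in an open-label trial. No section says the coordinator performs sputum induction, and the Induced Sputum section sets the same 2-minute interruptions for everyone.

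The reply does not remove the dependence itself. The safeguards reduce the chance of learning a first arm but do nothing about what that arm then reveals. The end-of-study question on perceived treatment would pick up participants' awareness, but not prediction by staff.

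**Conclusion.** The point holds as an avoidable design weakness whose effect is contingent. Given a known arm and a tracked order within the stratum, blocks of 2 reveal the partner with probability 1.00, where blocks of 4 would predict the second allocation with probability 0.67. The 50% share (24 to 25 of 50) is a ceiling and not an expected rate. How often an arm would be learned cannot be derived from the document.

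The exposure lies mainly in selection at enrolment and in questioning about adverse events and antibiotics, the latter through the censoring rule; any effect on SGRQ and BCSS is indirect. The laboratory measurement of biomass is not directly exposed, and the power figures in Table 1 are unaffected. The change is worth making because it is cheap; leaving it undone would not by itself invalidate the trial.

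**What to change.** In Randomization procedure, replace the fixed block size of 2 with blocks whose size varies at random between 4 and 6 within each inhaled-corticosteroid stratum. State in the protocol only that permuted blocks of varying size are used, and record the sizes in the Research Pharmacist's file alone.

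This costs a regenerated list and one amended sentence. The statistical price is a possible imbalance of up to 3 participants per stratum, where blocks of 2 allow at most 1. At 20 evaluable per group, the 17/23 worst case takes power for the diversity measure at a difference of 0.22 from about 0.675 to 0.665. The document gives no variance for biomass, so the same calculation cannot be made for the primary outcome.
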